9.3.2.6 Risk Assessment for Tumor Lysis Syndrome for Patients Treated with Venetoclax

Patients enrolling in Cohort B will be assessed for TLS risk and categorized in a risk category at screening as described below:

1. **Low-risk** category: the presence of all measurable lymph nodes with the largest diameter <5 cm by radiologic assessment* baseline AND absolute lymphocyte counts <25 ×10⁹/L
2. **Medium-risk** category: the presence of all measurable lymph nodes with the largest diameter ≥5 cm and <10 cm by radiologic assessment* OR absolute lymphocyte count ≥25 ×10⁹/L
3. **High-risk** category: the presence of any lymph node with the largest diameter ≥10 cm by radiologic assessment* OR the presence of BOTH an absolute lymphocyte count ≥25 ×10⁹/L AND a measurable lymph node with the largest diameter ≥5 cm by radiologic assessment*.

* Baseline CT/MRI scan at screening as defined in [Footnote_7](#) to Table 10.

Reassessment of the patient's risk category should be performed before first and each subsequent dose escalation of venetoclax on C1D8, C1D15, C1D22, C2D1 and C2D8 based upon blood chemistry, tumor burden (ALC, physical examination), comorbidities or symptoms suggestive of TLS. In cases when an unscheduled visit needs to be performed during ramp-up phase of venetoclax (e.g., due to dosing interruption or reduction of venetoclax which leads to changed treatment schedule of venetoclax), no risk reassessment for TLS needs to be performed at respective regular visit(s) when MOR00208 is administered. Furthermore, during the safety run-in phase of Cohort B discussion will occur between the Investigator and sponsor's medical monitor regarding the plan for TLS prophylaxis, including hydration, as necessary.

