8.5.2 Prophylaxis for Tumor Lysis Syndrome in Cohort B

Patients enrolling in Cohort B will be assessed for TLS risk and categorized in a risk category at screening. Prior to the initiation of the first doses of MOR00208 medical prophylaxis for TLS should be initiated according to the institutional standard of care.

Administration of venetoclax can cause rapid reduction in tumor and thus poses a risk for TLS in the initial 5-week ramp-up phase with venetoclax. Changes in blood chemistries consistent with TLS that require prompt management can occur as early as 6 to 8 hours following the first dose and at each dose increase. The risk of TLS is a continuum based on multiple factors, including tumor burden and comorbidities. Therefore, tumor burden assessments, including radiographic evaluation (e.g., CT scan), blood chemistry (potassium, uric acid, phosphorus, calcium, and creatinine) should be performed in all patients and the pre-existing abnormalities should be corrected prior to initiation of treatment with venetoclax. Reduced renal function (creatinine clearance [CrCl] <80 mL/min) further increases the risk. The risk may decrease as tumor burden decreases. [Table 5](#) describes the recommended TLS prophylaxis and monitoring during treatment with venetoclax based on tumor burden determination from clinical trial data. Importantly, all patients in Cohort B, who participate in the safety run-in phase, will be hospitalized on the day of the first two dose escalations of venetoclax (C1D8 and C1D15).

Table 5: Recommended TLS Prophylaxis Based on Tumor Burden From Clinical Trial Data of Venetoclax

Tumor Burden		Prophylaxis		Blood Chemistry Monitoring ^{c,d}
		Hydration ^a	Antihyperuricemics	Setting and Frequency of Assessments
Low	All LN <5 cm AND ALC <25 x10 ⁹ /L	Oral (1.5-2 L)	Allopurinol ^b	Outpatient 
 • Pre-dose, 6 to 8 hours, 24 hours at first dose of 20 mg and 50 mg • Pre-dose at subsequent ramp-up doses
Medium	Any LN 5 cm to <10 cm OR ALC ≥25 x10 ⁹ /L	Oral (1.5-2 L) and consider additional intravenous	Allopurinol	Outpatient 
 • Pre-dose, 6 to 8 hours, 24 hours at first dose of 20 mg and 50 mg • Pre-dose at subsequent ramp-up doses • Consider hospitalization for patients with CrCl <80mL/min at first dose of 20 mg and 50 mg; see below for monitoring in hospital

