High	Any LN ≥10 cm OR ALC ≥25 x10 ⁹ /L AND any LN ≥5 cm	Oral (1.5-2 L) and intravenous (150-200 mL/hr as tolerated)	Allopurinol; consider rasburicase if baseline uric acid is elevated	In hospital at first dose of 20 mg and 50 mg 
 • Pre-dose, 4, 8, 12 and 24 hours Outpatient at subsequent ramp-up doses 
 • Pre-dose, 6 to 8 hours, 24 hours

Note: Consider all patient comorbidities before final determination of prophylaxis and monitoring schedule.

^aAdminister intravenous hydration for any patient who cannot tolerate oral hydration.

^bStart allopurinol or xanthine oxidase inhibitor 2 to 3 days prior to initiation of venetoclax.

^cEvaluate blood chemistries (potassium, uric acid, phosphorus, calcium, and creatinine); review in real time.

^dFor patients at risk of TLS, monitor blood chemistries at 6 to 8 hours and at 24 hours at each subsequent ramp-up dose

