8.10.1 Management of Tumor Lysis Syndrome

Background: Tumor lysis syndrome is an important identified risk when initiating venetoclax. In the initial Phase 1 dose-finding trials, which had shorter (2-3 week) ramp-up phase and higher starting dose, the incidence of TLS was 12% (9/77; 4 laboratory TLS, 5 clinical TLS), including 2 fatal events and 3 events of acute renal failure, 1 requiring dialysis. The risk of TLS was reduced after revision of the dosing regimen and modification to prophylaxis and monitoring measures. In venetoclax clinical trials, patients with any measurable lymph node ≥ 10 cm or those with both an ALC $\geq 25 \times 10^9/L$ and any measurable lymph node ≥ 5 cm were hospitalized to enable more intensive hydration and monitoring for the first day of dosing at 20 mg and 50 mg during the ramp-up phase. In 66 patients with CLL starting with a daily dose of 20 mg and increasing over 5 weeks to a daily dose of 400 mg, the rate of TLS was 6%. All events either met laboratory TLS criteria (laboratory abnormalities that met ≥ 2 of the following within 24 hours of each other: potassium >6 mmol/L, uric acid >476 $\mu\text{mol/L}$, calcium <1.75 mmol/L, or phosphorus >1.5 mmol/L); or were reported as TLS events. The events occurred in patients who had a lymph node(s) ≥ 5 cm or ALC $\geq 25 \times 10^9/L$. No TLS with clinical consequences such as acute renal failure, cardiac arrhythmias or sudden death and/or seizures was observed in these patients. All patients had CrCl ≥ 50 mL/min.

Based on the results of the phase I clinical study of MOR00208 in patients with CLL/SLL and the preliminary results of the MOR208C201 and MOR208C202 studies, the anticipated possible risks associated with administration of MOR00208 to patients include TLS with a suspected relationship to MOR00208 treatment. In the phase I trial of MOR00208 in patients with CLL/SLL one patient did develop TLS which required rasburicase and intravenous fluids, however, subsequent infusions were tolerated without incident. It is notable that this patient had received no prior chemotherapy and had been treated only with single agent CD20 antibody therapy prior to receipt of MOR00208.

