Management: Patients enrolling in Cohort B will be assessed for TLS risk and should receive appropriate prophylaxis for TLS as described in detail in Section 8.5 and 9.3.3.6. Importantly, all patients in Cohort B, who participate in the safety run-in phase, will be hospitalized on the day of the first two dose escalations of venetoclax (C1D8 and C1D15). Nephrology or acute dialysis service should be consulted or contacted on admission per institutional standards to ensure emergency dialysis is available and the appropriate staff is aware and prepared to handle any necessary intervention for TLS.

MOR00208 should be withheld for any events of clinical TLS (clinical TLS is defined as laboratory TLS with clinical consequences such as acute renal failure, cardiac arrhythmias, or sudden death and/or seizures). After resolution MOR00208 therapy may be resumed at the discretion of the physician.

During the ramp-up phase with venetoclax blood chemistries should be monitored and abnormalities should be managed promptly. Dosing should be interrupted if needed. More intensive measures should be employed (intravenous hydration, frequent monitoring, hospitalization) as overall risk increases. For any events of clinical TLS, resume venetoclax at a reduced dose following resolution. Concomitant use of venetoclax with strong or moderate CYP3A inhibitors or inducers within 7 days prior to the first dose of venetoclax and during ramp-up phase of venetoclax is contraindicated. P-gp and BCRP inhibitors increases venetoclax exposure may increase the risk of TLS; therefore, concomitant use of venetoclax with P-gp and

BCRP inhibitors at initiation and during ramp-up phase should be avoided and requires venetoclax dose adjustment.

Patients should be advised of the potential risk of TLS to immediately report any signs and symptoms associated with this event (fever, chills, nausea, vomiting, confusion, shortness of breath, seizure, irregular heartbeat, dark or cloudy urine, unusual tiredness, muscle pain, and/or joint discomfort) to their doctor for evaluation, and to be adequately hydrated every day when taking venetoclax to reduce the risk of TLS.

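### Protocol 9.3.2.6 defines Medium TLS risk by all measurable nodes where Table 5 says any, so one kind of Cohort B patient has no risk class at screening (minor)

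*Protocol*

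**What the plan says.** Two places in the protocol define the TLS risk class for patients starting venetoclax.

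- **Section 9.3.2.6** says that patients entering Cohort B are given a risk category at screening. Item 2 (Medium) reads "the presence of all measurable lymph nodes with the largest diameter ≥5 cm and <10 cm" by radiologic assessment, or ALC at or above 25 ×10⁹/L. An asterisk ties the node measurement to the baseline CT/MRI scan.
- **Section 8.5.2, Table 5**, sets prophylaxis and monitoring by tumor burden. Its Medium row reads "Any LN 5 cm to <10 cm OR ALC" at or above 25 ×10⁹/L.

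The Low and High definitions agree between the two places. Low is all nodes below 5 cm and ALC below 25. High is any node of 10 cm or more, or ALC of at least 25 together with a node of at least 5 cm.

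Section 8.10.1 says that Cohort B patients "should receive appropriate prophylaxis for TLS as described in detail in Section 8.5", which is where Table 5 sits. Its other pointer, to 9.3.3.6, leads to the section on minimal residual disease. Section 9.2.8 cites 8.5, 8.10.1 and 9.3.2.6 together for unscheduled visits in the ramp-up. No sentence says which definition prevails.

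**The concern.** A classification rule used for safety should place every patient it covers in a class. With *all* in the Medium line, a patient whose nodes fall partly below 5 cm and partly between 5 and 10 cm, with a low ALC, meets no line of the section that is meant to classify them. A site working from 9.3.2.6 would have to leave the class open or infer it, while a site working from Table 5 would record Medium. TLS is the main risk of starting venetoclax, so the two definitions should not disagree. At stake is one consistent class at the screening assessment.

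**Working it through.** The plan gives no figure to reproduce, so the check is logical.

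**Inputs.** The three lines of Section 9.3.2.6 and the three tumor-burden rows of Table 5, as set out above.

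**One patient.** Nodes of 7 cm and 3 cm, ALC 10 ×10⁹/L, under 9.3.2.6:

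- Low fails: 7 cm is not below 5 cm.
- Medium fails: 3 cm is not at least 5 cm, so not all nodes are in range, and 10 is below 25.
- High fails: no node reaches 10 cm, and 10 is below 25.

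Under Table 5 the 7 cm node alone makes the patient Medium.

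**All profiles.** There are three node-size bands: below 5, 5 to below 10, and 10 cm or more. A patient with at least one measurable node has one of 2³ − 1 = 7 combinations of bands. With two ALC bands this gives 7 × 2 = 14 profiles. A patient who meets both Medium and High is taken as High.

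| Node sizes present | ALC <25: 9.3.2.6 | ALC <25: Table 5 | ALC ≥25: 9.3.2.6 | ALC ≥25: Table 5 |
|---|---|---|---|---|
| Only <5 cm | Low | Low | Medium | Medium |
| Only 5 to <10 cm | Medium | Medium | High | High |
| Both <5 and 5 to <10 cm | **none** | Medium | High | High |
| Any with ≥10 cm (4 combinations) | High | High | High | High |

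- Table 5: 1 Low + 3 Medium + 10 High = 14, none unclassified.
- 9.3.2.6 as written: 1 Low + 2 Medium + 10 High = 13, so 1 of 14 is unclassified.
- 9.3.2.6 with *any* in item 2: identical to Table 5, 0 of 14 unclassified.

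Patients with no measurable node are left out, because neither place says how *all* applies to them. Counting them adds two profiles, and the gap is then 1 of 16 before the change and 0 of 16 after it.

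**Which quantifier fits the rest of the section.** The High line of 9.3.2.6 needs only one node of at least 5 cm once ALC reaches 25. The 7 cm and 3 cm patient is therefore High at ALC 25 and has no class at ALC 24. Under Table 5 the same step is from High to Medium.

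**Side effect of the change.** Profiles that meet both the Medium and the High line go from 6 of 14 to 8 of 14. Table 5 already has 8 of 14, so the change creates no overlap that Table 5 lacks.

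**What the class alters in practice.** The Low and Medium rows of Table 5 differ in two items, both discretionary:

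- Hydration. Medium is "Oral (1.5-2 L) and consider additional intravenous".
- Setting. Medium adds "Consider hospitalization for patients with CrCl" below 80 mL/min, at the first 20 mg and 50 mg doses.

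The second item is already covered. Section 8.5.2 hospitalizes every Cohort B run-in patient on C1D8 and C1D15, which are the 20 mg and 50 mg steps. Section 7.1 puts 10 to approximately 12 patients in the run-in, out of approximately 12 planned for the cohort. What mainly remains is additional intravenous hydration.

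**The case against.** The strongest reply is that nobody would be misled. Table 5 gives the answer, Section 8.10.1 sends the reader there for prophylaxis, and a patient who is neither Low nor High can sensibly be taken as Medium. Item 2 could also be read as referring to the largest diameter across all nodes, which closes the gap. During the run-in the investigator and medical monitor discuss the prophylaxis plan, hydration included. A note to Table 5 adds "Consider all patient comorbidities before final determination of prophylaxis and monitoring schedule". Among the 66 patients on the 20 mg to 400 mg ramp-up described in Section 8.10.1, "No TLS with clinical consequences such as acute renal failure, cardiac arrhythmias or sudden death and/or seizures was observed in these patients".

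Most of this stands, and it is why the point is minor. It does not make item 2 correct. Both rescuing readings are inferences that 9.3.2.6 does not state. The 66 patients limit the severity only loosely: their 6% TLS rate covers a mixed group, with the events in patients who had a node of at least 5 cm or ALC of at least 25, and is not specific to this profile.

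Three stronger readings are tempting, and the documents do not support them.

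- *Such patients would miss prophylaxis.* Table 5 sets prophylaxis and classes them as Medium.
- *The gap recurs at all six scheduled assessments (screening and five dose steps).* The node criterion rests on the baseline scan. The five reassessments rest on blood chemistry, ALC, physical examination, comorbidities and symptoms, and no CT is scheduled between screening and C4D1.
- *The TLS listing would be incomplete or inconsistent.* SAP Appendix F gives only the title of Listing 16.2.9.6. Neither its columns nor the eCRF page is shown.

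**Conclusion.** Item 2 of Section 9.3.2.6 is wrong as written and contradicts Table 5. The gap is exactly one profile: at least one node of 5 to below 10 cm, at least one measurable node below 5 cm, none of 10 cm or more, and ALC below 25 ×10⁹/L. It arises mainly at the screening assessment. The fraction 1 of 14 counts profiles and says nothing about how many patients would fall there.

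Severity is minor. No endpoint, analysis set or sample size depends on the class. The conclusion rests on reading *all measurable lymph nodes* literally. The minor rating rests on Table 5 governing prophylaxis and on the run-in making up essentially the whole of Cohort B.

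**What to change.** In item 2 of Section 9.3.2.6 only, replace *the presence of all measurable lymph nodes* with *the presence of any measurable lymph node*. Leave the Low line, the High line and Table 5 as they are. Check that the eCRF risk-assessment page, which is not among the documents, uses the same wording. A sentence saying that High takes precedence over Medium is optional, since Table 5 has the same overlap.

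The cost is one phrase and one form check, which can go into the next amendment. It adds no procedure, visit or patient.

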9.3.2.7 Adverse Events

Please refer to Section 10 (Safety Monitoring).

9.3.3 Assessment of Efficacy

9.3.3.1 Tumor Response Assessment

Criteria of the International Workshop on Chronic Lymphocytic Leukemia (IWCLL) for CLL subjects (Hallek et al., 2008) will be used to determine rates of response and progression for patients with CLL, with the modification that treatment-related lymphocytosis (Note: PRL is applicable in Cohort A only) in the absence of other signs or symptoms of disease progression will not be considered as progressive disease (Cheson et al., 2012; Hallek et al., 2012; NCCN NHL 2015 Guidelines). For patients with SLL, assessments will be performed using the Lugano Classification criteria for SLL subjects (Cheson et al., 2014).

The secondary endpoint overall response rate (ORR) will be derived from the local review of radiology and clinical data.

Patients who develop a PR will be assessed using MRD testing from peripheral blood as well as from bone marrow, in case PB MRD negativity status was reached. Furthermore, patients who develop a complete response as per standard criteria will be investigated using MRD testing and bone marrow aspiration/biopsy as described in IWCLL (Hallek et al., 2008).

Overall response assessments include physical exams, recording of symptoms, radiographic and hematological evaluations to evaluate for both AEs and for disease progression per the schedule of assessments. If a patient shows signs of progression, the patient may continue on treatment until progression is confirmed by CT scan. The CT scan should be performed and collected with resolution sufficient to allow accurate and consistent comparison of target lesion measurements with subsequent CT scans. The same scan modality should be used for all assessments, and all patients are required to have scans of the neck/chest/abdomen/pelvis.

Baseline tumor assessments must be performed a maximum of 14 days before C1D1. As response is a secondary endpoint of the trial and that PD will be followed by physical examination, CT scans performed prior to screening as part of the regular clinical work-up of the patient will be allowed up to 6 weeks before C1D1. This is to prevent the re-irradiation of patients who have recently undergone a CT scan. However, a CT scan must be performed within the 14 day period prior to C1D1 for those patients with signs of rapidly progressing disease at screening.

MRI may be used in lieu of CT for patients with contraindications to the administration of contrast agents, or due to other medical reasons, at the same timepoints as CT or, in addition to CT, at the discretion of the Investigator (in this case, MRI may be performed as/when appropriate). The method used at baseline should be used throughout the study unless otherwise medically indicated.

Any suspected case of disease progression should be confirmed with a CT scan. Radiological assessment of efficacy response will be required to be reviewed at C4D1, C7D1, C13D1, C19D1, etc., and at the EOT visit (in case the last tumor evaluation was not performed within 28 days). There is a time window of ± 7 days for the assessments on Cycle 4 and Cycle 7 and ± 14 days window for the following examinations. Patients should continue to be followed and adhere to study-related procedures until progression has been confirmed.

A CT/MRI scan has to be performed at least 8 weeks after CR was identified by clinical criteria (and before a BM biopsy is obtained for CR confirmation). Clinical criteria should be based on physical examination and/or laboratory values.

In case of this confirmatory CT/MRI scan the following shall apply:

- If a regular CT/MRI scan is scheduled within less than 8 weeks after identification of the CR by clinical criteria, then this examination should be postponed to meet the confirmation timeline of at least 8 weeks.

and/or

- The following regular CT/MRI scan can be postponed/skipped, if this examination is within 8 weeks of the CR confirmatory scan.

9.3.3.2 Tumor Response Assessment for CLL

Definitions of Tumor Response and Progression

Responses will be categorized locally as CR, PR, PRL, SD, or PD.
(Note: PRL is applicable in Cohort A only.)

The best overall response in the course of the study will be determined. The best overall response is the best response recorded from the start of treatment until disease progression, withdrawal from study or death (taking as a reference for disease progression the smallest measurements recorded since treatment started).

At baseline, up to 6 lymph nodes should be selected as index lesions that will be used to quantitate the status of the disease during study treatment. Ideally, the index lesions should be located in disparate regions of the body. However, it is optimal if mediastinal and retroperitoneal areas of disease are assessed whenever these sites are involved. Any other measurable and abnormal nodal lesions not selected for quantitation as index lesions may be considered non-index lesions. In addition, non-measurable evidence of CLL such as nodal lesions with both diameters < 1.0 cm, extranodal lesions, bone lesions, leptomeningeal disease, ascites, pleural or pericardial effusions, lymphangitis of the skin or lung, abdominal masses that are not confirmed and followed by imaging techniques, cystic lesions, previously irradiated lesions, and lesions with artifacts may be considered as non-index disease. The presence or absence of non-index disease should be recorded at baseline and at the stipulated intervals during treatment. The non-

index disease at baseline will be used as a general reference to further characterize regression or progression of CLL during assessments of the overall tumor response during treatment. Measurements are not required and these lesions should be followed as “present” or “absent”.

A table of response definition by the IWCLL 2008 is provided in [Appendix J](#).

Complete Response

To satisfy criteria for a CR, all of the following criteria must be met:

- No evidence of new disease
- ALC in peripheral blood of $< 4 \times 10^9/L$
- Regression of all index nodal masses to normal size ≤ 1.5 cm in the longest diameter (LDi)
- Normal spleen and liver size
- Regression to normal of all nodal non-index disease and disappearance of all detectable non-nodal, non-index disease
- Morphologically negative bone marrow defined as $< 30\%$ of nucleated cells being lymphoid cells and no lymphoid nodules in a bone marrow sample that is normocellular for age
- Peripheral blood counts meeting all of the following criteria:
 - ANC $> 1.5 \times 10^9/L$ without need for exogenous growth factors (e.g., G-CSF)
 - Platelet count $\geq 100 \times 10^9/L$ without need for exogenous growth factors
 - Hemoglobin ≥ 110 g/L (11.0 g/dL) without red blood cell transfusions or need for exogenous growth factors (e.g., erythropoietin)

Subjects who fulfill all the criteria for a CR (including bone marrow criteria) but who have a persistent anemia, thrombocytopenia, or neutropenia or a hypocellular bone marrow that is related to prior or ongoing drug toxicity (and not to CLL) will be considered as a CR with incomplete marrow recovery (CRi).

Partial Response

To satisfy criteria for a PR, all of the following criteria must be met:

- A decrease in the number of blood lymphocytes by 50% or more from the value before therapy
- Reduction in lymphadenopathy by CT scans as defined by the following:
 - A decrease in lymph node size by 50% or more either in the sum products of up to 6 lymph nodes, or in the largest diameter of the enlarged lymph node(s)
 - No increase in any lymph node, and no new enlarged lymph node. In small lymph nodes (< 2 cm), an increase of less than 25% is not considered to be significant
- A reduction in the noted pretreatment enlargement of the spleen or liver by 50% or more, as detected by CT scan
- The blood count should show one of the following results:
 - Neutrophils more than $1.5 \times 10^9/L$ ($1500/\mu L$) without need for exogenous growth factors
 - Platelet counts greater than $100 \times 10^9/L$ ($100,000/\mu L$) or 50% improvement over baseline without need for exogenous growth factors
 - Hemoglobin greater than 110 g/L (11.0 g/dL) or 50% improvement over baseline without requiring red blood cell transfusions or exogenous erythropoietin

Stable Disease

To satisfy criteria for SD, the following criteria must be met:

- No evidence of new disease
- There is neither sufficient evidence of tumor shrinkage to qualify for PR nor sufficient evidence of tumor growth to qualify for definitive PD

Definitive Progressive Disease

The occurrence of any of the following events indicates definitive PD:

- Evidence of any new disease:
 - A new node that measures > 1.5 cm in the longest diameter (LD) and > 1.0 cm in the longest perpendicular diameter (LPD)
 - New or recurrent splenomegaly, with a minimum longest vertical dimension (LVD) of 14 cm
 - New or recurrent hepatomegaly, with a minimum LVD of 20 cm
 - Unequivocal reappearance of an extranodal lesion that had resolved
 - A new unequivocal extranodal lesion of any size
 - New non-index disease (e.g., effusions, ascites, or other organ abnormalities related to CLL)

Isolated new effusions, ascites, or other organ abnormalities are not sufficient evidence alone of a PD unless histologically confirmed. Thus, a declaration of PD should not be made if this is the only manifestation of apparently new disease.

- Evidence of worsening of index lesions, spleen or liver, or non-index disease:
 - Increase by $\geq 50\%$ from the nadir in the sum of the products of the perpendicular diameters (SPD) of index lesions
 - Increase from the nadir by $\geq 50\%$ in the LD of an individual node or extranodal mass that now has an LD of > 1.5 cm and an LPD of > 1.0 cm
 - Splenic progression, defined as an increase in splenic enlargement by $\geq 50\%$ from nadir (with a minimum 2 cm increase and a minimum LVD of 14 cm)
 - Hepatic progression, defined as an increase in hepatic enlargement by $\geq 50\%$ from nadir (with a minimum 2 cm increase and a minimum LVD of 20 cm)
 - Unequivocal increase in the size of non-index disease (e.g., effusions, ascites, or other organ abnormalities related to CLL)
 - Transformation to a more aggressive histology (e.g., Richter's syndrome) as established by biopsy (with the date of the biopsy being considered the date of CLL progression if the subject has no earlier objective documentation of CLL progression).
- Decrease in platelet count or hemoglobin that is attributable to CLL, is not attributable to an autoimmune phenomenon, and is confirmed by bone marrow biopsy showing an infiltrate of clonal CLL cells
 - The current platelet count is $< 100 \times 10^9/L$ and there has been a decrease by $> 50\%$ from the highest on-study platelet count
 - The current hemoglobin is < 110 g/L (11.0 g/dL) and there has been a decrease by > 20 g/L (2 g/dL) from the highest on-study hemoglobin

If there is uncertainty regarding whether there is true progression, the subject should continue study treatment and remain under close observation. In particular, worsening of constitutional symptoms in the absence of objective evidence of worsening CLL will not be considered definitive disease progression; in such subjects, both CLL-related and non-CLL-related causes for the constitutional symptoms should be considered. Worsening of disease during temporary interruption of study treatment (e.g., for intercurrent illness) is not necessarily indicative of resistance to study treatment. In these instances, CT or MRI or other relevant evaluations should be considered in order to document whether definitive disease progression has occurred. If subsequent evaluations suggest that the subject has experienced persistent definitive CLL progression, then the date of progression should be the timepoint at which progression was first objectively documented.

Lymphocytosis During Therapy

Upon initiation of idelalisib treatment, transient increase of absolute lymphocyte count is expected in most patients because idelalisib can mobilize CLL cells from tissues into the peripheral blood. This characteristic pharmacological action can be prominent early in therapy but can persist over time and should not be confused with disease progression in subjects who have persistent control of other CLL-related signs and symptoms. **In the absence of other objective evidence of disease progression, lymphocytosis alone will not preclude subjects from meeting the criteria for PR if other criteria for PR are met and will not be considered evidence of disease progression if occurring in isolation.** Thus, subjects with worsening lymphadenopathy, organomegaly, bone marrow involvement, progressive cytopenias, appearance of new disease, or transformation to a more aggressive lymphoid malignancy histology (e.g., Richter's syndrome) will be considered to have progressed according to IWCLL criteria for progressive disease. Subjects with lymphocytosis without any of these other events will not be considered to have progressed and should be continued on study drug until the occurrence of definitive disease progression (Note: PRL is applicable in Cohort A only).

